6.4.2 Secondary Efficacy Endpoints

All assessments will be based on investigator assessments of tumor response/recurrence/progression and cause of death. The secondary efficacy endpoints for this study are as follows.

- CR at the 3-month disease assessment, evaluated by both cystoscopy and cytology.
- Duration of CR will be defined for patients with a CR as the time from the first occurrence of a documented complete response to recurrence of high-grade NMIBC or death from any cause. Data for patients without an event will be censored at the last date known to be alive and recurrence free.
- RFS rate at 6, 12, and 18 months, defined as the proportion of patients who are alive and free of persistent/recurrent high-grade NMIBC. Data for patients without an event will be censored at the last date known to be alive and free of persistent/recurrent NMIBC.
- Bladder-intact DFS will be defined as the time from the first study treatment to earliest evidence of progression to muscle-invasive disease in the bladder, regional pelvic progression, distant metastasis, bladder cancer–related death, or cystectomy. Data for patients without an event will be censored at the last date known to be alive and event-free. Data for patients who died from causes other than bladder cancer will be censored at the day of death.

- PFS, defined as the time from the first study treatment to the first occurrence of progression to muscle-invasive disease based on cystoscopy and urine cytology or death from any cause. Data for patients without a PFS event will be censored at the last date known to be alive and progression-free.
- Cystectomy-free survival, defined as from start of study treatment to bladder removal for any cause or death from any cause. Data for patients alive without cystectomy will be censored at the last date known to be alive without cystectomy.
- Overall survival, defined as the time from the first dose of study treatment to death from any cause. Data for patients who have not died will be censored at the last date known to be alive.

Data for patients without the respective post-baseline assessment will be censored at the time of start of treatment plus one day. Time-to-event endpoints (duration of CR, bladder-intact DFS, PFS, cystectomy-free survival, and overall survival) will be summarized by cohort with use of the Kaplan-Meier method. Kaplan-Meier curves will be presented. Kaplan-Meier estimates of event rates at landmark timepoints (e.g., 6-, 12-, and 18-months) and median time to the event will be presented with the corresponding 95% CI. RFS rates and the corresponding 95% CI will be summarized at the 6-, 12-, and 18-month timepoints.

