3.5.4 Efficacy Outcome Measures

The primary efficacy outcome measure for this study is as follows:

- CR at the 6-month evaluations after the start of study treatment. Patients must be evaluated for CR by both cystoscopy and cytology and bladder biopsies will be required for the 6-month CR disease assessment.

The secondary efficacy outcome measures for this study are as follows:

- CR at the 3-month disease assessment, evaluated by both cystoscopy and cytology.
- Duration of CR, defined as time from first occurrence of a documented CR until the time of recurrence of NMIBC or death from any cause
- RFS rate at 6, 12, and 18 months, defined as the proportion of patients who are alive and free of persistent/recurrent high-risk NMIBC
- Bladder-intact DFS, defined as time from first study treatment to earliest evidence of progression to muscle-invasive disease in the bladder, regional pelvic progression, distant metastasis, bladder cancer–related death, or cystectomy or death from any cause
- PFS, defined as the time from first study treatment to the first occurrence of progression to muscle-invasive disease or death from any cause
- CFS, defined as the time from first study treatment to cystectomy or death from any cause
- Overall survival, defined as the time from first study treatment to death from any cause

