6.4 EFFICACY ANALYSES

6.4.1 Primary Efficacy Endpoint

The primary efficacy outcome measure for this study is CR at 6 months after the start of study treatment as assessed by the investigator on the basis of cystoscopic assessment and urine cytology. The CR rate will be summarized by timepoint for each cohort, and the corresponding 95% CI will be calculated on the basis of the Clopper-Pearson method.

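### Duration of CR and RFS in Section 6.4.2 do not count progression to muscle-invasive or metastatic disease as an event, and the synopsis, Section 3.5.4 and Section 6.4.2 name different disease for both endpoints

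*Combined protocol and SAP*

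**What the plan says.** For complete responders, Section 6.4.2 defines duration of CR as the "time from the first occurrence of a documented complete response to recurrence of high-grade NMIBC or death from any cause". It defines RFS at 6, 12 and 18 months as the "proportion of patients who are alive and free of persistent/recurrent high-grade NMIBC", and then says that patients without an event are "censored at the last date known to be alive and free of persistent/recurrent NMIBC". At the end of the section, duration of CR is on the list of endpoints to be summarised by Kaplan-Meier. RFS is not on that list, and no method is named for its rates or confidence intervals.

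Section 3.5.4 and the synopsis use other words. There, duration of CR runs "until the time of recurrence of NMIBC or death from any cause", with no grade given, and RFS is the "proportion of patients who are alive and free of persistent/recurrent high-risk NMIBC".

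Elsewhere in Section 6.4.2 progression is an event. Bladder-intact DFS lists muscle invasion, regional pelvic progression and distant metastasis, and PFS lists muscle invasion.

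**The concern.** Muscle-invasive and metastatic disease are by name not non-muscle-invasive disease. A definition that ends only at high-grade NMIBC or death therefore leaves out the outcome that Section 1.1.1 calls the main worry in these patients. If such a patient is censored at progression, the censoring is tied to a bad outcome and the Kaplan-Meier estimate is too high. If RFS is a simple proportion, the same patient can be counted as a success.

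The differing disease terms add a second problem. Two analysts could take the same data, follow different sections of the protocol, and report different durations of response.

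**Working it through.** The plan gives no figure for these endpoints, so there is nothing to reproduce. The check is a comparison of the text, followed by an illustration with assumed event counts.

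**Is progression covered anywhere?** Section 4.5.5 spells out high-grade NMIBC as any T1, high-grade Ta or CIS. Sections 4.5.5 and 4.6.2 list muscle-invasive or metastatic progression as a separate reason to stop treatment. The opening sentence of Section 6.4.2 mentions progression, but it says who assesses it, not which endpoints it ends. No other section adds it to duration of CR or RFS. Three groups are already counted as events: patients with high-grade NMIBC documented first, patients whose CIS never cleared (persistent disease, for RFS), and patients who die. The gap is the living patient who cleared and then progressed directly.

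**Duration of CR.** Assume n responders, r = 2 high-grade recurrences, one direct progressor, and full follow-up of all others to the timepoint.
- Progressor counted as an event: (n − 3)/n.
- Progressor censored after both recurrences: (n − 2)/n.
- Progressor censored before both: (n − 3)/(n − 1).

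| Responders (from Table 12) | Censored before both | Censored after both | Counted |
|---|---|---|---|
| 10 | 7/9 = 77.8% | 8/10 = 80.0% | 7/10 = 70.0% |
| 18 | 15/17 = 88.2% | 16/18 = 88.9% | 15/18 = 83.3% |

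**RFS as a proportion.** Each direct progressor counted as recurrence-free adds 1/N: 1/20 = 5 points, 1/10 = 10 points. N=10 is the planned size of Cohort 2 or 3. N=20 is reached only if the whole expansion of about 10 goes to one of them. If the censoring sentence is instead taken to mean a time-to-event analysis, the patient is censored. With N=20 and 6 other events (assumed) that gives 13/19 = 68.4% to 14/20 = 70.0%, against 13/20 = 65.0% if counted. The two readings are alternatives and do not add.

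**Wording.**

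| Endpoint | Synopsis and 3.5.4 | 6.4.2 |
|---|---|---|
| Duration of CR | NMIBC, unqualified | high-grade NMIBC |
| RFS, definition | high-risk NMIBC | high-grade NMIBC |
| RFS, censoring date | none given | NMIBC, unqualified |

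The terms are not synonyms. Under Section 1.1.1, high-risk also takes in low-grade Ta that is at once multiple, recurrent and larger than 3 cm. Low-grade pTa is compatible with CR (Sections 3.1.2 and 4.5.5), yet Section 3.1.2 also describes low-grade papillary disease as recurrent. With 10 responders, 2 high-grade recurrences and one low-grade pTa recurrence (assumed), duration of CR is 8/10 = 80% under Section 6.4.2. It is 7/10 = 70% if the term in Section 3.5.4 is taken to mean any grade.

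**The case against.** **Size and likelihood.** The route is narrow. Every patient enters with CIS, so a missed patient must first clear it and then progress with no T1, high-grade Ta or CIS recorded. The only progression rates offered, 5%-17% in Section 1.1.1, are for all progression in two very-high-risk groups. They bear on Cohort 3 at most and do not say what share is direct. One patient in 20 moves RFS by 5 points, while Table 12 gives 14/20 an interval of 46% to 88%. Bladder-intact DFS already captures these patients. All of this stands and limits the severity. None of it supplies the missing event, and investigators recording muscle invasion as a recurrence would be an unwritten convention.

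**Wording.** Ending a CR for low-grade pTa would sit badly with the CR definition, and Section 6.4.2, the operative analysis text, says high-grade. The unqualified term in the RFS censoring sentence may be shorthand for the high-grade disease named just before it. That is the likely intent, but the sections still disagree on their face.

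**A stronger reading of RFS.** Because RFS carries a censoring rule, a reader might infer that it should become a Kaplan-Meier endpoint. The documents do not support that. Sections 3.1.2 and 4.5.5 let persistent high-grade disease without progression at week 12 stay on treatment, and Section 3.4.7 expects responses to rise between 3 and 6 months. A time-to-event RFS would make week-12 persistence an irreversible failure. One patient who clears by month 6 would then cost 5 points at N=20 or 10 points at N=10.

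**Conclusion.** The point holds as a gap and an inconsistency in definitions, with low severity. As written, a living direct progressor is censored for duration of CR and can be counted as recurrence-free for RFS, and both errors are in the favourable direction. Per such patient, the illustration gives 78-80% instead of 70% for duration of CR with 10 responders and 2 recurrences, and 5 or 10 points for RFS at N=20 or N=10. The counts are assumed, the effect is zero with no direct progressors, and the documents give no frequency for them.

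A reader might infer that the trial's main efficacy result, or the decision to open Cohorts 2 and 3, is compromised. The documents do not support that. Both endpoints are descriptive, no stated decision rule uses them, and the 6-month CR rate does not depend on them.

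**What to change.** 1. In Section 6.4.2, add progression to muscle-invasive, regional pelvic or metastatic disease as an event for duration of CR and as a failure for RFS.
2. Use one definition, high-grade recurrence or progression, in the synopsis, Section 3.5.4 and Section 6.4.2. State that low-grade pTa does not end a CR.
3. Keep RFS as a landmark proportion at 6, 12 and 18 months, so that disease persisting at week 12 but cleared by the landmark is not a failure. Align the censoring sentence with that definition or remove it, and give a Clopper-Pearson interval as Section 6.4.1 does for the CR rate. If the sentence is removed, say how a patient with no assessment at a landmark is counted.

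The cost is text in three places. Progression dates are already needed for bladder-intact DFS. Estimates may be slightly less favourable. Under Section 4.5.11, protocol tumor assessments after stopping treatment continue only for patients who stopped for reasons other than recurrence, progression or cystectomy. Later progression is therefore counted only as far as it is collected, and the report should say so.

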Approximately 70% of NMIBC presents as predominantly Ta disease, 20% of patients present with predominantly T1 disease, and 10% present as predominantly CIS. CIS is considered a distinct entity because of the difficulty in detection with standard cystoscopy examination and its high propensity for disease progression (Nese et al. 2009). Primary CIS occurs in approximately 3% of all UC; however, it is found concurrently with T1 disease in up to 50% of cases (Kim and Steinberg 2001). The presence of CIS is associated with a high incidence of progression to invasive disease, even after surgical and intravesical therapy. The rate of disease progression to muscle invasion with or without TURBT with CIS has been shown to be 50%–60% (Casey et al. 2015). In a single institution, where a series of 155 patients with CIS were managed with TURBT and intravesical bacille Calmette-Guérin (BCG), the 5-year cumulative incidence of progression to T1 or higher disease was 45% (95% CI: 37–55). In this study, it was observed that diffuse involvement of the mucosa with CIS was associated with a particularly aggressive disease, with disease progression in 60%–80% of such patients (Chade et al. 2010). From a therapeutic perspective, NMIBC is broadly categorized into low-risk and intermediate/high-risk, on the basis of the risk of recurrence and/or disease progression (Babjuk et al. 2011).

High-risk NMIBC is characterized by any one or more of the following:

- T1 tumor
- High-grade tumor
- CIS
- Multiple and recurrent and large (> 3 cm) low-grade Ta lesions (all 3 conditions must be met for low-grade Ta lesions).

These tumors are at high-risk of recurrence and progression, with progression to muscle invasive disease being the primary concern (Sylvester et al. 2006; Babjuk et al. 2013).

The European Association of Urology (EAU) describes a group of patients with NMIBC that falls into an extremely high-risk group, hereafter referred to as “very high-risk” (VHR) NMIBC (Babjuk et al. 2013). These include patients with any of the following:

- Multiple and/or large (> 3 cm) high-grade T1 tumors
- High-grade T1 tumors with concurrent CIS
- High-grade T1 tumors with CIS in the prostatic urethra
- Micropapillary variant NMIBC

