4.5.5 Tumor and Response Evaluations

Screening and tumor response assessment will be in accordance with national (EAU AUA, and NCCN) guidelines, which recommend cystoscopic examination and urine cytology every 12 weeks for the first 2 years, and every 24 weeks thereafter (or as clinically appropriate) until 5 years, and then yearly. Upper tract imaging with CT urography or intravenous pyelogram will be performed at the 6- and 18-month disease assessments. Annual upper tract imaging thereafter is recommended as clinically indicated.

Screening assessments must include imaging of the upper tract collecting system, which may include any one or more of the following: intravenous pyelogram, CT urography, renal ultrasound with retrograde pyelogram, ureteroscopy, or magnetic resonance imaging urogram. Pelvic CT before TURBT may be considered, but is not required.

Primary assessment of tumor (at screening and while on study) will be with cystoscopy and urine cytology.

White-light cystoscopy, narrow band imaging cystoscopy, or fluorescent (blue-light) cystoscopy will be acceptable for baseline assessment. The same methodology used to assess disease sites at screening should be used throughout the study except when medical contraindicated (e.g., the same cystoscopy protocol and urine examination).

The Sponsor may replace patients who have had a change in the type of cystoscopy (e.g., screening with white-light cystoscopy and follow-up evaluation with blue-light cystoscopy) to ensure consistent evaluation over time. All known sites of disease must be documented at screening and re-assessed at each subsequent tumor evaluation. A Bladder Map template ([Appendix 11](#)) has been provided and should be used to document the approximate size and location of abnormalities observed at screening, baseline, and on study cystoscopy/TURBT assessments.

Mandatory bladder biopsies will be performed at the 6-month tumor assessment. In absence of visible tumor, template biopsies should be obtained from all quadrants of the bladder. Template biopsies may be performed under anesthesia, at the discretion of the investigator. Regions of the template biopsies should include the trigone, left lateral wall, right lateral wall, posterior wall, and dome. Where feasible, the same evaluator should perform assessments if possible to ensure internal consistency across visits.

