Appendix 1 Schedule of Assessments: Cohort 1A

Study Procedures	Screening Days –28 to –1	Weeks 1–96 ^a	Disease Progression	Treatment Completion/ DC Visit ^b	Follow-Up
Signed Informed Consent Form ^c	x				
Review of eligibility criteria	x				
Medical, surgical, and cancer histories ^d	x				
Demographic ^e	x				
ECOG performance status	x	x ^f		x	
Complete physical examination ^g	x				
Limited physical examination ^h		x ^f		x	
Weight	x				
Height	x				
Vital signs ⁱ	x	x ^f		x	
12-lead ECG ^j	x				
Upper tract imaging with CT urography or IV pyelogram ^{k, l}	x	Prior to atezolizumab treatment Cycles 9 and 29, then annually as indicated			
Hematology ^{m, n}	x ⁿ	x ^f		x	
Serum chemistry ^{n, o}	x ⁿ	x ^f		x	
Coagulation panel (aPTT, INR) ⁿ	x ⁿ			x	
Urinalysis ^{n, p}	x				
Creatinine clearance	x				
TSH, free T3, free T4	x	q6w [C2D1 and then every other cycle thereafter (e.g., C4D1, C6D1, etc.)]			
HIV, HBV, HCV serology ^q	x				

Appendix 1
Schedule of Assessments: Cohort 1A (cont.)

Study Procedures	Screening Days –28 to –1	Weeks 1–96 ^a	Disease Progression	Treatment Completion/ DC Visit ^b	Follow-Up
TB test ^r	x				
Serum pregnancy test ^{n, s}	x	q3w ^f		x	
Archival/screening FFPE tumor tissue specimen or 10 unstained slides ^t	x				
Serum PK sample ^u		See Appendix 4			
Serum ATA sample ^u		See Appendix 4			
Plasma PD biomarker		See Appendix 4			
Atezolizumab infusion ^v		x			
Tissue biopsy (mandatory sample) ^w		Prior to Cycle 9 (before Week 24)			
Tumor biopsy (optional sample)			x	x	x
Tumor assessment ^x	x	Every 12 weeks ^{x, l}		x	x ^y
Patient reported outcomes ^z		Cycle 1 Day 1, Cycle 2 Day 1, and every 6 weeks thereafter		x	
Concomitant medications ^{aa}	x ^{aa}	x		x	
Adverse events ^{bb}	x ^{aa}	x		x	x
Survival and anti-cancer therapy follow-up assessment ^{cc}					x
Blood samples for pharmacodynamics and biomarkers ^{dd}		See Appendix 4			

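### Duration of CR can start at an unbiopsied Month 3 CR, so CIS missed then and found at the Month 6 biopsy is counted as a response followed by a recurrence

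*Combined protocol and SAP*

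**What the plan says.** - **Start and event.** Section 6.4.2 measures duration of CR as the "time from the first occurrence of a documented complete response to recurrence of high-grade NMIBC or death from any cause". It does not restrict the starting CR to a particular visit or to one with a biopsy.
- **Month 3.** Section 3.5.4 lists "CR at the 3-month disease assessment, evaluated by both cystoscopy and cytology". The CR definition in Sections 3.1.2 and 4.5.5 accepts a normal-looking bladder with non-positive cytology.
- **Month 6.** Section 4.5.5 states: "Mandatory bladder biopsies will be performed at the 6-month tumor assessment". Section 3.5.4 adds that "bladder biopsies will be required for the 6-month CR disease assessment". Appendices 1, 2 and 3 schedule one mandatory on-study biopsy, before atezolizumab Cycle 9; other biopsies are as clinically indicated or at the investigator's discretion.
- **Population.** All patients must have CIS at entry (Section 3.1.1). Section 1.1.1 says that "CIS is considered a distinct entity because of the difficulty in detection with standard cystoscopy examination".
- **Wording that points the other way.** For Cohorts 1B, 2 and 3, Section 3.1.2 gives Weeks 10, 22, 46, 70 and 94 as examples of when biopsies fall relative to BCG. The appendices contain no biopsy visit at Weeks 10, 46, 70 or 94.

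**The concern.** The Month 3 and Month 6 assessments do not look equally hard for disease. Where no tumor is visible at Month 6, template biopsies are still taken, so that visit searches for occult disease; Month 3 has no scheduled equivalent. Because duration of CR may start at Month 3, persistent CIS that neither cystoscopy nor cytology shows is recorded first as a response and then, once biopsied, as a recurrence. No rule in Section 6.4.2 classes that finding as persistence.

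At stake is a secondary endpoint. The Kaplan-Meier curve for duration of CR could drop at about 12 weeks for reasons unrelated to relapse, and its denominator would include patients who are not responders on the primary endpoint. Cohorts 2 and 3 plan about 10 patients each and Cohort 1A up to about 12, so one such patient is visible on the curve.

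**Working it through.** **The plan's own figures.** The documents give no number for this point. The only efficacy figures are the Clopper-Pearson intervals in Tables 11 and 12. All 11 rows reproduce to the whole percent (for example 8/20 gives 19.1% to 64.0%, against the stated 19% to 64%). No arithmetic is in dispute.

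**One patient followed through the definitions (Cohorts 1B, 2, 3).**
1. Week 10: CIS present, bladder looks normal, cytology not positive. The patient meets the CR definition, and duration of CR starts.
2. Week 22: the mandatory biopsy shows CIS. The patient is not a 6-month CR.
3. Section 6.4.2: CIS is high-grade disease, so a duration-of-CR event is recorded 22 − 10 = 12 weeks after the response.

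If the missed CIS has instead truly cleared by Month 6, there is no event; the CR is dated about 12 weeks before it was confirmed.

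**Illustration of size.** Inputs, all assumed:
- t = 0.40, true clearance at Month 3
- m = 0.10, 0.20 or 0.30, the share of persistent CIS missed by cystoscopy and cytology together
- c = 0 or 0.50, the share of missed CIS that truly clears by Month 6
- the Month 6 biopsy finds all remaining CIS

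Formulas:
- apparent Month 3 CR = t + (1 − t)m
- false share of Month 3 responders = (1 − t)m / [t + (1 − t)m]
- artefact recurrences at Month 6 = (1 − c) × false share

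For m = 0.20: 0.40 + 0.60 × 0.20 = 0.52; 0.12 / 0.52 = 23.1%; with c = 0.50, 11.5%.

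| m | Apparent Month 3 CR | False share | Artefact recurrences, c = 0 | Artefact recurrences, c = 0.50 |
|---|---|---|---|---|
| 10% | 46% | 13.0% | 13.0% | 6.5% |
| 20% | 52% | 23.1% | 23.1% | 11.5% |
| 30% | 58% | 31.0% | 31.0% | 15.5% |

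With no true recurrence at all, the Kaplan-Meier estimate at 12 weeks would be 87.0%, 76.9% or 69.0% for c = 0, and 93.5%, 88.5% or 84.5% for c = 0.50.

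**Scale in a cohort of 10.** Four true responders plus one missed case make five Month 3 responders. That one case alone takes the curve to 4/5 = 80% at Month 6.

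**Effect on the median.** Assume also an exponential true median of 52 weeks, and c = 0. For m = 0.20 the curve after Week 12 is (0.40/0.52) × 0.5^(u/52). Setting this to 0.5 gives u = 52 × log2(0.769/0.5) = 32.3 weeks. For m = 0.10 and 0.30 the medians are 41.5 and 24.1 weeks. Measured from Month 6 among 6-month responders, the same model gives 52 weeks, because the exponential has no memory.

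**The case against.** **The biopsy schedule may not be as stated.** Section 3.1.2 names Week 10 as an example biopsy week, Section 3.4.7 ties on-treatment biopsy timing to the end of BCG induction, and the tumor-assessment footnotes mention random biopsies of all quadrants. This stands as an unreconciled text. In context the weeks describe timing relative to BCG and the footnotes describe technique, while the same paragraph of Section 3.1.2 mandates only the 6-month biopsy. If Week 10 biopsies were in fact required, the problem would be confined to Cohort 1A.

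**The size is assumed.** This stands. The statement in Section 1.1.1 concerns cystoscopy alone. CR also needs non-positive cytology, unclear cytology is repeated, abnormal findings can prompt biopsy, and narrow-band and blue-light cystoscopy are allowed. Only CIS hidden from both tests counts. Section 3.4.7 also says maintenance BCG raises response between Months 3 and 6, so some missed CIS may clear, though Cohort 1A receives no BCG.

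**First documented CR is a defensible start, and anchoring at Month 6 has its own bias.** This also stands. Patients who truly relapse or die between Months 3 and 6 drop out of a 6-month set. In the illustration the Month 6 anchor lengthens the median from 32.3 to 52 weeks. It should therefore stand beside the planned analysis and not replace it.

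**The 3-month result is already labelled.** It is. Section 3.5.4 names its tests, and although "The CR rate will be summarized by timepoint for each cohort", no trend test is planned. None of this says how a Month 6 biopsy finding enters duration of CR.

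**Conclusion.** The point holds for duration of CR. As written, Section 6.4.2 counts persistent CIS that was missed at Month 3 and found at Month 6 as a response followed by a relapse. Under the assumed 40% clearance and 10 to 30% miss rate, 13 to 31% of Month 3 responders would be false. The share appearing as artefact recurrences is the same if none clears by Month 6, and 6.5 to 15.5% if half do. The direction follows from the definitions; the amount cannot be derived from the documents. This is a low-cost improvement to a secondary analysis.

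Three stronger readings are tempting and not supported:
- **That the primary endpoint is biased.** Section 3.5.4 requires biopsies for the 6-month CR, so this mechanism does not reach it. I read that section as making a positive Month 6 biopsy a non-response, although Section 6.4.1 names only cystoscopy and cytology.
- **That the imaging schedule adds to the problem.** Section 4.5.5 says "Upper tract imaging with CT urography or intravenous pyelogram will be performed at the 6- and 18-month disease assessments", but upper-tract imaging is not the test for CIS in the bladder, and the CR definition counts it only where performed.
- **That the RFS rates suffer the same error.** RFS already treats persistent disease as an event, so no patient passes from response to recurrence, and its 6-month landmark coincides with the biopsy. Later visits follow the surveillance pattern cited in Sections 1.1.3.1 and 4.5.

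**What to change.** 1. In Section 6.4.2, keep duration from the first documented CR and report beside it duration from the biopsied 6-month CR, among 6-month responders.
2. Add a sensitivity analysis of the first-CR version: high-grade disease first shown by the Month 6 biopsy, after a Month 3 CR without biopsy, is classed as persistence, and the patient leaves the duration set.
3. State the limits of both. The 6-month version is conditional on still being in CR at Month 6, omits true relapses between Months 3 and 6, and may give a longer cohort median. The sensitivity analysis cannot separate missed CIS from a true relapse in that interval.
4. Reconcile the example biopsy weeks in Section 3.1.2 with Appendices 1 to 3, which schedule only the Month 6 biopsy.

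The cost is analysis wording, one additional summary and one sensitivity analysis on data already collected. No visit, procedure or treatment rule changes.

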4.2 METHOD OF TREATMENT ASSIGNMENT AND BLINDING

This is an open-label study. The investigator will determine the appropriate cohort for each patient.

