6.5 SAFETY ANALYSES

Safety will be assessed through summaries of adverse events, changes in laboratory test results, and changes in selected vital signs. Safety analyses will be performed for treated patients by cohort. Selected analyses will be performed by BCG dose level.

All adverse events with onset on or after treatment on Day 1 (treatment-emergent adverse events) will be summarized by mapped term, appropriate thesaurus levels, and NCI CTCAE v4 toxicity grade. All adverse events, NCI CTCAE v4 Grade ≥ 3 adverse events, adverse events leading to withdrawal of treatment and serious adverse events will be summarized overall and for treatment related events. In addition, all deaths including cause of death will be summarized. All adverse events and deaths will be listed.

All DLTs will be listed for DLT-evaluable patients (see Section 3.1.3 for a definition of DLT-evaluable patients).

NCI CTCAE v4 Grade 3 and 4 laboratory data will be listed; in addition changes in selected laboratory data will be summarized by grade with use of the NCI CTCAE v4. Selected vital signs and selected laboratory data will be summarized. The incidence of antibodies to atezolizumab will be summarized.

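### Bladder-intact DFS counts death from any cause in the synopsis and Section 3.5.4, but Section 6.4.2 censors deaths not due to bladder cancer

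*Combined protocol and SAP*

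**What the plan says.** The synopsis (Efficacy Outcome Measures) and Section 3.5.4 define bladder-intact DFS in identical terms. The clock runs from first study treatment to the earliest of muscle-invasive progression in the bladder, regional pelvic progression, distant metastasis or death related to bladder cancer, and the list closes with "or cystectomy or death from any cause".

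Section 6.4.2 gives the same list but stops at cystectomy. It adds: "Data for patients who died from causes other than bladder cancer will be censored at the day of death".

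The same section states that "All assessments will be based on investigator assessments of tumor response/recurrence/progression and cause of death". Section 4.2 states that "This is an open-label study". The time-to-event endpoints, bladder-intact DFS among them, "will be summarized by cohort with use of the Kaplan-Meier method", and the planned output includes "Kaplan-Meier estimates of event rates at landmark timepoints", with 6, 12 and 18 months given as examples.

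For comparison, Section 6.4.2 defines cystectomy-free survival as running to "bladder removal for any cause or death from any cause". Duration of CR, PFS and overall survival in that section also count death from any cause.

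**The concern.** One named endpoint has two incompatible event rules. A patient who dies of another cause, with no earlier progression or cystectomy, has an event under Section 3.5.4 and a censored time under Section 6.4.2. All the passages are current text. None says which prevails, and neither rule is called a sensitivity analysis.

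Two things are at stake:

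- **Interpretation.** A programmer following Section 6.4.2 will produce a curve that a reader holding the 3.5.4 definition will misread, in the favourable direction.
- **Dependence on attribution.** Under 6.4.2 the result turns on the cause of death that the investigator assigns. Under 3.5.4 attribution makes no difference.

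If the choice is left until data are in hand, it could also be made with the results in view.

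**Working it through.** **The plan's own figures.** The documents state no event count, rate or power for bladder-intact DFS, so there is nothing to reproduce for this endpoint. The only planning figures, the Clopper-Pearson intervals in Tables 11 and 12 (Section 6.1), were recomputed, and all 11 match after rounding.

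**Direction of the difference.** Let E be a disease or cystectomy event and D an other-cause death in a patient who has not yet had E. At a time with n at risk, d1 of type E and d2 of type D, the Kaplan-Meier factors are:

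- Section 6.4.2: 1 − d1/n
- Section 3.5.4: 1 − (d1 + d2)/n

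Both rules remove the patient at the same time, so the risk sets are the same. The 6.4.2 curve can never be lower. It is strictly higher once a D has occurred, unless it has already reached zero. With no D the curves coincide.

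**Size, with assumed counts.** Cohorts 2 and 3 are planned at about 10 patients each (Section 3.1.1), and Table 12 uses a maximum of 20. The event counts and times below are assumptions.

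*Example 1: n = 10, three E, one D, complete follow-up to the landmark.*

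| Position of D | Section 6.4.2 | Section 3.5.4 |
|---|---|---|
| Before any E | 6/9 = 66.7% | 6/10 = 60.0% |
| After one E | 0.9 × 6/8 = 67.5% | 60.0% |
| After two E | 0.8 × 6/7 = 68.6% | 60.0% |
| After three E | 7/10 = 70.0% | 60.0% |

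As event rates this is 30.0% to 33.3% against 40.0%.

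*Example 2: same cohort, but the investigator attributes that death to bladder cancer.* Both rules give 6/10 = 60.0%. One attribution moves the 6.4.2 result by 6.7 to 10.0 points and the 3.5.4 result by nothing.

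*Example 3: n = 10 with censoring.* E at months 3, 8 and 14, D at month 10, two patients censored at month 12.5, four followed past month 18.

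- 6 months: 9/10 = 90.0% under both.
- 12 months: 6.4.2 gives 9/10 × 8/9 = 80.0%; 3.5.4 gives 9/10 × 8/9 × 7/8 = 70.0%.
- 18 months (five at risk at month 14): 0.80 × 4/5 = 64.0% against 0.70 × 4/5 = 56.0%.

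*Example 4: n = 20, six E, one D, complete follow-up.* 6.4.2 gives 13/19 = 68.4% (D first) to 14/20 = 70.0% (D last); 3.5.4 gives 13/20 = 65.0%.

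*Example 5: n = 10, one D, no E, complete follow-up.* 6.4.2 reports bladder-intact DFS of 100% beside PFS, cystectomy-free survival and overall survival of 90%. Under 3.5.4 all four are 90%.

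**Size over a range of risks.** Let a be the 18-month risk of E and b that of other-cause death, both assumed and independent. Event-free at 18 months is 1 − a under 6.4.2 and (1 − a)(1 − b) under 3.5.4, so the gap is (1 − a)b. For b from 3% to 15%, the gap is 2.1 to 10.5 points at a = 30% and 1.5 to 7.5 points at a = 50%.

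**Scale.** In Table 12, 12 responders out of 20 carry a 95% CI of 36% to 81%. That interval belongs to the CR rate and serves only as a guide to precision at this size. The gaps above are well inside it.

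**The case against.** The conflict in wording is not disputed. The strongest case against giving it weight has five parts.

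- **Low stakes.** This is one of seven secondary endpoints, with no test, sample-size role or decision rule. The difference is zero without such a death and below sampling error with one. All of this stands and limits the severity. It does not excuse two definitions: a confidence interval displays sampling error but not a mismatch of definition.
- **The illustrations assume a death in a small cohort.** The nearest figures are the Grade 5 adverse events in Table 3: 4/119 (3.4%), 3/310 (1.0%) and 1/95 (1.1%). At 1.0% to 3.4%, the chance of at least one such death among 10 patients is about 9% to 29%. Those patients had advanced or metastatic disease, and median treatment in the first two groups was 12 to 15 weeks, so the rates do not transfer. The point that the examples are conditional on a death is fair.
- **The rule for patients with no post-baseline assessment.** Section 6.4.2 censors them one day after treatment starts. Read literally, a death before the first cystoscopy (Week 10 in Appendix 3) would be dropped under either definition, and the gap for that death would vanish. The natural reading is that the rule gives a censoring date to patients without an event, not that it discards a known death. A clarifying clause would still help.
- **Open-label attribution.** With no randomized comparison, and with progression, metastasis and cystectomy already events, cause of death matters only when death comes first. That is correct and makes this a side issue.
- **A cause-specific endpoint is legitimate.** It may sit beside all-cause ones, and the 6.4.2 rule is explicit. The synopsis and 3.5.4 wording is redundant, since any-cause death already contains bladder cancer death. Section 6.4.2 may therefore be what was intended. The documents do not settle this, which is why both repairs are offered.

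**Conclusion.** The concern holds. The synopsis and Section 3.5.4 contradict Section 6.4.2 on whether an other-cause death is an event. Whenever such a death precedes the patient's own event and falls on or before the landmark, the planned Kaplan-Meier estimate departs from the 3.5.4 endpoint, upward for event-free survival, unless the 6.4.2 curve is already at zero.

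Under the assumed counts, one such death raises the event-free estimate by 6.7 to 10.0 points in 10 patients (8.0 points at 18 months in the censored example) and by 3.4 to 5.0 points in 20. These sizes rest on invented event counts, because the documents supply none. The direction rests on no such assumption.

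This should be fixed but is not critical. The primary 6-month CR rate and the sample size do not change. Other-cause deaths remain visible elsewhere: in overall survival, in PFS and cystectomy-free survival when death is the first event, and in the safety section, where "all deaths including cause of death will be summarized".

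**What to change.** Before analysis, adopt one definition in the synopsis, Section 3.5.4 and Section 6.4.2.

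- **To keep the 3.5.4 endpoint:** add death from any cause to the event list in 6.4.2 and delete the sentence that censors other-cause deaths. It would also help to say that the censoring rule for patients without a post-baseline assessment applies only to patients without an event.
- **To keep the 6.4.2 rule:** remove death from any cause from the synopsis and 3.5.4, and label the endpoint as cause-specific. A cumulative-incidence summary with other-cause death as a competing event is then an optional addition.

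Either route costs a few words and needs no new data. The one downside of the first is that the reported event-free rate may look less favourable if other-cause deaths occur.
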